#### 12.5.1 Primary Efficacy Endpoint

The primary efficacy endpoint will be HAMD17 total score change from baseline to 60 hours post-infusion (on Day 3) for the IV only cohorts and to Day 29 for the IV to Oral cohort. Although the trial is not powered for inferential analysis and there is no consideration for control of type 1 error across multiple cohorts, a clinically meaningful numeric difference in means of 3-4 points between ganaxalone and placebo treatment groups would be considered an indication of efficacy and will be the most influential outcome in the overall assessment of the efficacy of ganaxalone in treating PPD.

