### 9.5.8 Efficacy Analyses

### 9.5.8.1 Primary Endpoint

The primary efficacy endpoint will be HAMD17 total score change from baseline to 60 hours post-infusion (on Day 3) for Cohorts 1-3 and to Day 29 for Cohort 6. The primary analysis in each cohort will be done using the mITT set. Although the trial is not powered for inferential analysis and there is no consideration for control of type 1 error across multiple cohorts, a clinically meaningful numeric difference in means of 3-4 points between ganaxalone and placebo treatment groups would be considered an indication of efficacy and will be the most influential outcome in the overall assessment of the efficacy of ganaxalone in treating PPD.

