# 6.0 Study Design

### 6.1 General Description

This is a Phase 2A, double-blind, placebo-controlled, multiple-dose escalation study consisting of up to 6 cohorts (Cohort 1 to 6).

Approximately 200 women with PPD 18–45 years of age will be screened to randomize up to 100 subjects across up to 6 cohorts, with Cohorts 4 and 5 optional. Approximately 10-30 subjects will be randomized into each cohort. Randomized subjects will receive ganaxolone or matching placebo in a 1:1 ratio. The study will be conducted in the United States at approximately 15 investigative sites.

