# 10.2 Analyses After Cohorts 1-3

An unblinded analysis of efficacy and safety data for Cohorts 1-3 will be conducted after the last patient in Cohort 3 has completed her final visit (or withdrawn from the study), all clinical data have been entered into the data capture system, AE and concomitant medication data have been coded, quality control checks have been completed, all data queries have been resolved, protocol deviations and the per protocol analysis set have been identified, and the database has been locked. TFLs for subject disposition, demographics and baseline characteristics, efficacy, and AEs will be produced external to PRA.

The continuing trial subsequent to Cohort 3 will again be conducted in a double-blind fashion.

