# 12.0 Statistical Methods

Data analyses will primarily be descriptive. The purpose of this study is to identify a ganaxolone dose and exposure level that is safe and well tolerated. Efficacy data will be collected but will be considered hypothesis-generating; i.e., there are no *a priori* hypotheses on which the study was powered. Results from exploratory statistical analyses may be presented but only to aid in interpretation.

Unless otherwise indicated, continuous variables will be summarized with the following descriptive statistics: n (number of observations), (arithmetic) mean, standard deviation (SD), first and third quartiles (Q1 and Q3), minimum (min) value, median, and maximum (max) value. The minimum and maximum values will be displayed to the same level of precision as the raw data, the median and mean to a further decimal place and the SD to two additional decimal places – up to 4 decimal places total.

Categorical data will be summarized with frequencies and percentages. Percentages by categories will be based on the number of subjects exposed within a treatment. Percentages will be rounded to one decimal place.

All analyses will use SAS version 9.4 or higher. Tables will present data summarized by treatment group within cohort. For each summary table, corresponding supportive listing(s) will be provided.

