### 12.5 Efficacy Analyses

Statistical analysis of efficacy endpoints will primarily be done using the mITT set and will be done only to aid in interpretation as the trial was not powered for inferential hypothesis testing. As such, there will be no adjustments for inflation of type 1 error due to multiplicity.

For efficacy endpoints expressed as continuous variables, summary tables will show continuous summary statistics for each time point of data collection (visit) as well as least squares (LS) means with standard errors (SEs) and associated p-values from mixed model repeated measures (MMRM) analysis. Summary statistics by time point will also be displayed graphically using bar and/or line charts. MMRM models will include fixed effects for treatment, visit, and the treatment-by-visit interaction, and the baseline observation will be included as a covariate. Repeated measurements are made on each subject. Residuals will be evaluated for substantial departure from normality and independent and constant variance. Methods such as data transformation, detecting and assessing the influence of outliers, and alternative analytical approaches (e.g., non-parametric) may be used to address assumption deviations. An unstructured covariance will be the default covariance structure but other structures (e.g., compound symmetry) may be used to evaluate sensitivity to the choice of structure or, if necessary, to achieve convergence. MMRM assumes missing observations are missing at random (MAR); i.e., missingness depends only on variables other than the outcome that are available in the database. Because the MAR assumption is not testable, and because it seems possible that subjects with poorer outcome may be more likely to miss trial assessments, a sensitivity analysis may be done in which all missing data will be imputed. Conservatively, multiple imputation with a pattern-mixture model will be used; specifically, for all subjects with missing observations regardless of treatment assignment, imputation will be based only on subjects randomized to placebo. The imputation method will be fully conditional specification (FCS) regression with 25 imputations. Variables in the imputer's model will be observed values at each time point included in the MMRM analysis, including baseline.

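### Does the 3-4 point HAMD17 criterion need a stated confidence interval and an estimate combining Cohorts 1-3?

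*SAP*

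**What the plan says.** SAP 12.5.1 states that "a clinically meaningful numeric difference in means of 3-4 points between ganaxalone and placebo treatment groups would be considered an indication of efficacy". Protocol 9.5.8.1 uses the same criterion and adds that it "will be the most influential outcome in the overall assessment of the efficacy of ganaxalone in treating PPD". In both places the sentence opens by conceding that the trial is not powered for inference and that type 1 error is not controlled across cohorts.

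The comparison is made cohort by cohort. Protocol 9.5.8.1 says "The primary analysis in each cohort will be done using the mITT set", and SAP 12.0 says "Tables will present data summarized by treatment group within cohort". On size, SAP 6.1 says "Approximately 10-30 subjects will be randomized into each cohort", with 1:1 allocation.

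For continuous endpoints SAP 12.5 plans "least squares (LS) means with standard errors (SEs) and associated p-values from mixed model repeated measures (MMRM) analysis". On model terms it says "MMRM models will include fixed effects for treatment, visit, and the treatment-by-visit interaction", with baseline as a covariate and no cohort term. SAP 10.2 says "An unblinded analysis of efficacy and safety data for Cohorts 1-3 will be conducted after the last patient in Cohort 3" and then describes timing and outputs, not a combined estimate. SAP 12.0 calls the efficacy data hypothesis-generating. The bodies of SAP 12.5.3 and protocol 9.5.8.3, both headed as exploratory, are not visible in this copy.

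**The concern.** The result given most weight for efficacy is a numeric threshold applied to a difference between two small groups, and the visible text attaches no interval to that difference. SAP 12.5 does not say whether its standard errors belong to each arm or to the difference, or which contrast the p-values test. Someone who saw only that the threshold was met could take noise for a signal. The results feed the choice of dose and regimen (protocol 2.1), and the sponsor may publish after any cohort (protocol 3.7).

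Cohorts 1-3 also each have their own concurrent randomised placebo group and the same +60h endpoint. An estimate stratified by cohort would keep those comparisons and be more precise than any one cohort, with no new data. Leaving it out looks like information wasted.

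**Working it through.** The plan gives no power, alpha or SD, so it has no figure of its own to reproduce.

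**Inputs.** Cohorts of 10 to 30 at 1:1 (SAP 6.1) give 5 to 15 per arm. The DRC recommended completing Cohort 3 with 20 women (protocol 1.2.1.4), so 10 per arm. The same section gives a preliminary review count of 12 for Cohort 2, so 6 per arm, possibly not final. For Cohort 1, 5 per arm is assumed (the low end of the range). The SD of HAMD17 change is assumed to be 6 to 10. The calculations are unadjusted; the planned baseline covariate would narrow the intervals somewhat.

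**One cohort.** SE = SD × √(2/n); 95% half-width = t(0.975, 2n-2) × SE.

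| n per arm | SD 6 | SD 8 | SD 10 |
|---|---|---|---|
| 5 | 8.75 | 11.67 | 14.58 |
| 10 | 5.64 | 7.52 | 9.40 |
| 15 | 4.49 | 5.98 | 7.48 |

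At 10 per arm and SD 8, 3.5 ± 7.52 gives -4.0 to 11.0.

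**Without assuming an SD.** The interval excludes zero only if the SD is below observed / (t × √(2/n)). At 10 per arm that limit is 3.19 for 3 points and 4.26 for 4 points. At 15 per arm it is 4.01 and 5.35.

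**Chance of meeting the threshold with no true effect.** 1 - Φ(3/SE). At 10 per arm and SD 8, SE = 3.58 and the chance is 0.20 in one cohort. For at least one of three such cohorts it is 1 - (1 - 0.201)³ = 0.49.

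**Can the reader recover the interval?** If the tabulated SEs are per arm, each is about 8/√10 = 2.53 at SD 8, and √(2.53² + 2.53²) = 3.58, the SE of the difference. If the SEs are already for the difference, no step is needed.

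**Combining Cohorts 1-3, stratified by cohort, with a common SD.** With N women per arm in total, SE = SD × √(2/N), df = 2N - 4. For 5 + 6 + 10 = 21 per arm:

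- SD 8: SE = 8 × √(2/21) = 2.47 against 3.58 for Cohort 3 alone; 1 - √(10/21) = 31% lower. Half-width 5.00 against 7.52.
- SD 6 and 10: half-widths 3.75 and 6.25.
- The weights are 5/21, 6/21 and 10/21, or 0.24, 0.29 and 0.48. True effects of 0, 0 and 4 give 4 × 10/21 = 1.90; effects of 4, 4 and 4 give 4.0.

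With 10 per arm in each cohort (N = 30) and SD 8, the SE is 2.07 and the half-width about 4.1.

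**The case for a change.** The case for a change is a fair one. A threshold of this weight deserves its uncertainty beside it, and an interval is estimation, so it sits at least as well with a plan that disclaims formal testing as the p-values already promised. The wording in SAP 12.5 on SEs and p-values is loose. The combined estimate would be supportive only, labelled as an average over regimens, and would preserve each cohort's randomised comparison.

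On the interval, the observation about precision stands. But SAP 12.5.1 itself names the quantity of interest, the ganaxolone-placebo difference in means. An analyst fitting the planned model with a treatment-by-visit term would estimate that contrast at the primary visit, and its SE comes with it. Adding the limits is a matter of layout: the estimate, its SE and the caveats around it are the same with or without them.

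On combining cohorts, the gain in precision stands; its usefulness does not. Protocol 3.4.1 to 3.4.3 target about 52, 100 to 120 and 180 ng/ml, and only Cohort 3 has a bolus. The stated purpose is to select a dose (protocol 2.1) and learn about dose-response (protocol 3.7), and an average describes none of the three regimens. Its weights also follow cohort size. Cohort 3's size was recommended by an unblinded committee after it had reviewed 13 women; the protocol mentions only adverse event data in that review, so bias is not shown, but the weights are not clearly fixed in advance. With analysis by cohort, the missing cohort term in the model is consistent with the rest of the plan.

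**Conclusion.** No change to the plan is called for.

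The missing interval is a gap in detail that analysts can fill from outputs already planned. Showing the per-cohort LS mean difference with its 95% limits would be a sensible choice when the tables are laid out. At 10 per arm, 3 points would exclude zero only with an SD below about 3.2, and 4 points only below about 4.3. The plan already treats the efficacy results as hypothesis-generating, so this imprecision contradicts nothing that it claims.

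The combined estimate is a trade-off that the plan can reasonably decline. It would cut the SE by about 31% against Cohort 3 alone (with 5, 6 and 10 per arm), but it answers a different question and could report 1.9 points when one regimen truly gives 4. At SD 8 it would still not exclude zero at 3.5 points; at SD 6 its half-width of 3.75 would just exclude zero at 4. Whether SAP 12.5.3 already contains such an analysis cannot be told from this copy.

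These figures rest on an assumed SD of 6 to 10, partly assumed sizes for Cohorts 1 and 2, and no baseline adjustment. A smaller SD would narrow the intervals: at 15 per arm, an observed 4 points would exclude zero with an SD below about 5.4. That would not alter the conclusion.

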#### 12.5.2 Secondary Efficacy Endpoints

The trial will also evaluate the following secondary endpoints at each post-baseline data collection time point to provide additional evidence of the efficacy of ganaxalone in treating PPD:

- Change from baseline in HAMD17 total score other than at 60 hours post-infusion (on Day 3) for Cohorts 1-3 and to Day 29 for Cohort 6
- HAMD17 response defined as at least a 50% reduction from baseline in total score
- HAMD17 remission defined as total score <= 7
- Change from baseline in EPDS total score
- Change from baseline in STAI6
- CGI-I rating

#### 12.5.3 Exploratory Efficacy Endpoints and Analyses

#### PRS 005 T 17 F

# 12.6 Safety Analyses

Unless otherwise stated in the subsections below, the following safety variables will presented in listings and analyzed in summary tables containing summary statistics and change from baseline by treatment arms for each study time point. All safety analyses will be based on the Safety Set.

- 1) Laboratory measures, including urine drug screen
- 2) Vital signs
- 3) Electrocardiogram (ECG)
- 4) Stanford Sleepiness Scale (SSS).

#### 12.6.1 Adverse Events

AEs reported from screening through EOS will be coded according to MedDRA® (Medical Dictionary for Regulatory Activities) version 20.0 or greater. Each reported AE will be mapped to a Preferred Term (PT) and a System Organ Class (SOC).

A treatment-emergent AE (TEAE) will be defined as an AE that began or worsened after the first dose of IP and no later than 30 days after the last dose of IP. AEs with insufficient date or time information to determine whether or not they were treatment-emergent will be considered treatment-emergent.

All TEAEs will be listed. In addition, separate listings will be done for non-treatment-emergent AEs and serious AEs (SAEs), treatment-emergent SAEs, and TEAEs that resulted in death, IP discontinuation, IP interruption, or dose reduction. Listings will include reported term, PT, and SOC; start and stop date; whether or not the AE was serious; severity; whether or not the AE was related to IP; action taken; and outcome.

Incidence and number of TEAEs will be summarized by SOC and PTs within SOCs. Summaries will include assessments of severity and relationship to IP. Missing severity will be considered severe and missing relationship will be considered related. Only the most related TEAE per subject for a given PT will be counted in summaries by relationship; similarly, only the most severe TEAE will be counted in summaries by severity. Separate summaries will be done for TEAEs related to IP and TEAEs resulting in IP discontinuation or interruption, or dose reduction. Summaries will be done separately for (a) all TEAEs and (b) treatment-emergent SAEs only.

#### 12.6.2 Laboratory Data

In addition to change from baseline summary tables for quantitative lab parameters, out of range lab observations will be determined using reference ranges provided by MedPace Laboratory and will be flagged in data listings.

Over the course of the study, there may be some lab tests performed that are not mentioned in the protocol. These tests will not be summarized but will be included in the listings.

Neurosteroid levels will be not be performed by PRA, as such, neurosteroid levels analysis details are beyond the scope of this statistical analysis plan.

PRS 005 T 17 F

### 12.6.3 Vital Signs

Vital signs will be analyzed as continuous variables. In addition to change from baseline summary tables, potentially clinically significant (PCS) observations will be flagged in data listings based on the criteria given in Table 3.

Vital Sign	Unit	Low PCS Criteria	High PCS Criteria
Heart rate	hom	≤50 and decrease of ≥15 from	≥120 and increase of ≥15 from
Healt fale	opin	baseline	baseline
Systolic blood	mmHa	≤90 and decrease of ≥20 from	≥180 and increase of ≥20 from
Pressure	IIIIIng	baseline	baseline
Diastolic		<eq and="" decrease="" of="">1E from</eq>	>10E and increase of >1E from
blood	mmHg	Source and decrease of 215 from	2105 and increase of 215 from
Pressure		baseline	baseline
Respiratory	Breaths/m	< 9 and decrease of >4 from baseline	≥30 and increase of ≥10 from
rate	inute	So and decrease of 24 from baseline	baseline
Body	Degree	≤36 and decrease of ≥1 from	≥38.3 and increase of ≥1 from
Temperature	Celsius	baseline	baseline
Body Weight	%	Decrease of ≥7 from baseline	Increase of ≥7 from baseline
Oximetry	%	≤90%	N/AA

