### 7.8.5.4 Vital Signs

Vital signs including blood pressure, pulse, respirations, temperature (recorded in Celsius [°C]) and pulse oximetry will be monitored at the time points as outlined above. Vital signs should be collected after the subject has been supine for 5 minutes. If a vital sign measurement is scheduled at the same time as a blood draw, vital signs should be collected prior to the blood draw. Blood pressure should be determined by an appropriately-sized cuff (using the same method, the same arm and in the same position throughout the study). Any abnormal screening vital sign results considered to be clinically significant should be repeated to confirm the finding. Height (in centimeters) will be collected at the screening visit. Weight (in kilograms) will be collected at the screening and 2 follow-up visits.

During the inpatient phase while the subject is receiving study drug subjects should be monitored for pulse oximetry continually, including during the nights. Monitoring may be interrupted for bathroom breaks, lunch etc.

If pulse oximetry drops below 91% the patient should be wakened and assessed for excessive sedation.

Any clinically significant deviations from baseline vital signs that are deemed clinically significant in the opinion of the investigator are to be recorded as an AE.

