### 8.1.5 Adverse Events Based on Clinical Laboratory and Other Safety Evaluations

A change in the value of a clinical laboratory, vital sign, or ECG assessment can represent an AE if the change is clinically relevant or if, during treatment with the investigational product, a shift of a parameter is observed from a normal value to an abnormal value, or a there is a further worsening of an already abnormal value. When evaluating such changes, the extent of deviation from the reference range, the duration until return to the reference range, either while continuing treatment or after the end of treatment with the investigational product, and the range of variation of the respective parameter within its reference range, must be taken into consideration.

If, at the end of the treatment phase, there are abnormal clinical laboratory, vital sign, or ECG values which were not present at the pretreatment value observed closest to the start of study treatment, further investigations should be performed until the values return to within the reference range or until a plausible explanation (e.g. concomitant disease) is found for the abnormal values.

CONFIDENTIAL

The investigator should decide, based on the above criteria and the clinical condition of a subject, whether a change in a clinical laboratory, vital sign, or ECG parameter is clinically significant and therefore represents an AE.

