### 9.5.7 Safety Analyses

Reported AE terms will be coded using the Medical Dictionary for Regulatory Activities (MedDRA). The incidence of Treatment Emergent AEs (TEAEs), defined as any AE that started or worsened after first administration of IP, will be summarized by treatment group, system organ class preferred terms, severity and relatedness for each cohort. SAEs and AEs leading to discontinuation of the study drug will be listed separately for each cohort.

The absolute values and change from baseline in laboratory tests, vital signs, SSS, ECGs and CSSRS will be summarized by treatment group for each cohort.

Potentially clinically important findings will be included in AE summaries and listings.

Results of the physical examination (baseline and discharge) will be listed.

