### 12.6.4.2 12-Lead ECG

12-lead ECG parameters will be analyzed and transferred externally to PRA. These parameters will be summarized as continuous variables. In addition to summary tables PCS ECG observations will be flagged in data listings based on the criteria given in Table 4.

ECG Parameter	Unit	Low PCS Criteria	High PCS Criteria
Heart rate	bpm	≤50 and decrease of ≥15 from baseline	≥120 and increase of ≥15 from baseline
PR Interval	ms	<120 and baseline value ≥120	>210 and baseline value ≤200
QRS Complex	ms	None	>110 and baseline value ≤110
QTcF	ms	None	Prolongation >30 from baseline

TABLE 4. ECG PCS CRITERIA

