Table 14.3.2.3.4	Incidence and Number of Treatment-Emergent Serious Adverse Events Resulting in Investigational Product Dose Reduction or Interruption	Safety
Table 14.3.2.3.5	Incidence of Treatment-Emergent Serious Adverse Event Preferred Terms in Order of Descending Incidence Among All Subjects	Safety
Table 14.3.3.1.X	Hematology Results by Time Point	Safety
Table 14.3.3.2.X	Biochemistry Results by Time Point	Safety
Table 14.3.3.3.X	Urinalysis Results by Time Point	Safety
Table 14.3.3.4.X	Urine Drug Screen by Time Point	Safety
Table 14.3.4.X	Vital Sign Results by Time Point	Safety
Table 14.3.5.X	Electrocardiogram Results	Safety
Table 14.3.6	Stanford Sleepiness Scale	Safety
Table 14.3.7.X	Columbia-Suicide Severity Rating Scale (C-SSRS) – Suicidal Ideation and Behavior by Time Point	Safety
Figure 14.2.1.1.1.1.1	Mean (SE) HAMD17 Total Score	mITT
Figure 14.2.1.1.1.3.1	Mean (SE) HAMD17 Total Score	mITT
Figure 14.2.1.1.2.1.1	Mean (SE) HAMD17 Bech Subscale (HAMD6)	mITT
Figure 14.2.1.1.2.3.1	Mean (SE) HAMD17 Bech Subscale (HAMD6)	mITT
Figure 14.2.1.1.3.1.1	Mean (SE) HAMD17 Anxiety Subscale	mITT
Figure 14.2.1.1.3.3.1	Mean (SE) HAMD17 Anxiety Subscale	mITT
Figure 14.2.1.1.4.1.1	Mean (SE) HAMD17 Gibbons Subscale	mITT
Figure 14.2.1.1.4.3.1	Mean (SE) HAMD17 Gibbons Subscale	mITT
Figure 14.2.1.1.5.4.1	Mean HAMD17 Individual Items	mITT
Figure 14.2.1.2.1.1	HAMD17 Total Score - Response	mITT
Figure 14.2.1.3.1.1	HAMD17 Total Score - Remission	mITT
Figure 14.2.2.1.1.1.1	Mean (SE) EPDS Total Score	mITT
Figure 14.2.2.1.1.3.1	Mean (SE) EPDS Total Score	mITT
Figure 14.2.2.1.2.1.1	Mean (SE) EPDS Anxiety Subscale	mITT
Figure 14.2.2.1.2.3.1	Mean (SE) EPDS Anxiety Subscale	mITT
Figure 14.2.2.1.3.4.1	Mean EPDS Individual Items	mITT
Figure 14.2.3.1.1.1.1	Mean (SE) STAI6 Total Score	mITT
Figure 14.2.3.1.1.3.1	Mean (SE) STAI6 Total Score	mITT
Figure 14.2.3.1.2.4.1	Mean STAI6 Individual Items	mITT

PRS 005 T 17 F

Page 33 of 35

Figure 14.2.4.1.1.1	CGI-Improvement	mITT
Figure 14.2.4.2.3.1	CGI-Improvement	mITT
Figure 14.3.6	Stanford Sleepiness Scale	Safety

List of End of Text Listings:			
Output	Title	Analysis Set	
Listing 16.1.7.X	Randomization Assignments	Screened	
Listing 16.2.1	Subject Disposition	Randomized	
Listing 16.2.2.X	Protocol Deviations	Randomized	
Listing 16.2.3.X	Subject Analysis Sets	Randomized	
Listing 16.2.4.1	Baseline Characteristics	Randomized	
Listing 16.2.4.2.X	Medical History	Safety	
Listing 16.2.4.3.X	Prior and Concomitant Medications	Safety	

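### The SAP uses its vital-sign and ECG outlier criteria only to flag listings, so no table counts by arm how many women met them

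*SAP*

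**What the plan says.** **Flags.** SAP 12.6.3 summarises vital signs as continuous variables and adds that "potentially clinically significant (PCS) observations will be flagged in data listings based on the criteria given in Table 3". SAP 12.6.4.2 does the same for ECG: "In addition to summary tables PCS ECG observations will be flagged in data listings based on the criteria given in Table 4".

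**By-arm tables.** Under SAP 12.6, laboratory, vital-sign, ECG and sleepiness data are "analyzed in summary tables containing summary statistics and change from baseline by treatment arms for each study time point". SAP 12.0 fills these tables with n, mean, SD, quartiles, minimum, median and maximum. Appendix 3 lists "Vital Sign Results by Time Point" and an ECG results table. It lists no table of women meeting a Table 3 or Table 4 criterion.

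**The protocol.** Section 9.5.7 states: "Potentially clinically important findings will be included in AE summaries and listings". It gives no thresholds and does not define the term.

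**The AE route.** Protocol 7.8.5.4 says that vital-sign deviations "deemed clinically significant in the opinion of the investigator are to be recorded as an AE". Under protocol 8.1.5 the investigator decides "whether a change in a clinical laboratory, vital sign, or ECG parameter is clinically significant and therefore represents an AE". Once an event is an AE, SAP 12.6.1 counts it: "Incidence and number of TEAEs will be summarized by SOC and PTs within SOCs".

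**Declared changes.** SAP 4.1 lists three changes from the protocol (C-SSRS, physical examination, Per Protocol Set). None concerns PCS values.

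**The concern.** Both documents give the study's purpose as finding a ganaxolone dose and exposure level that is safe and well tolerated. For a sedating drug, much of that evidence lies in individual excursions: a drop in oxygen saturation, a low respiratory rate, hypotension, a QTcF rise. The SAP took the step of fixing thresholds for such values in advance, then left them as marks on rows of a listing.

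At stake is a simple descriptive result: in each cohort, how many women on ganaxolone and how many on placebo crossed each pre-specified line. As planned, a reader of the study report would have to assemble that from listings. The only outlier counts by arm would be of findings that an investigator chose to report as AEs.

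**Working it through.** The documents state no figure on this point, so there is none to reproduce. The check is whether any planned output yields the count.

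**1. Where a flagged value can go.** It appears in a listing, with its flag. It may enter a by-time-point table as one of the values summarised. It enters a TEAE table only if the investigator judges it clinically significant. No SAP text carries a Table 3 or Table 4 flag into an AE summary or any other summary.

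**2. Two-part criteria.** The low systolic criterion in SAP Table 3 needs a value of 90 mmHg or less *and* a fall of 20 mmHg or more. Take three women in one arm at one time point. The readings are invented for illustration, built from those two figures (90 + 20 = 110; 110 + 20 = 130):

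| | Set A: baseline → reading (change) | Set B: baseline → reading (change) |
|---|---|---|
| Woman 1 | 110 → 90 (−20) | 90 → 90 (0) |
| Woman 2 | 130 → 130 (0) | 130 → 110 (−20) |
| Woman 3 | 90 → 110 (+20) | 110 → 130 (+20) |

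In both sets the baselines are 90, 110, 130, the readings are 90, 110, 130, and the changes are −20, 0, +20. Every statistic in SAP 12.0 is therefore identical for baseline, value and change. In Set A one woman meets the criterion; in Set B none does. Adding the same further women to both sets leaves this unchanged.

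**3. Repeat flags.** The oximetry criterion (90% or less) has one part. Suppose an arm of 10 has one flagged reading at each of three time points. If it is the same woman each time, the incidence is 1/10 = 10%. If three women are flagged once each, it is 3/10 = 30%. The three by-time-point tables can be the same in both cases.

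**4. Latest reading in the window.** SAP 8.4 analyses the latest observation when a window holds several. In Cohorts 1-5 the +8h window runs from 360 to under 600 minutes, which is 240 minutes or 4 hours. If a flagged reading at 480 minutes is followed by a normal recheck before 600, only the recheck enters the table. In Cohort 6 all Day 1 readings from the start of infusion share one window. Rechecks are foreseeable: protocol 7.8.5.4 has the woman wakened and assessed when oximetry is below 91%, and protocol 4.4.1 refers to a repeat ECG. This step assumes that both readings are recorded in the database.

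**5. Size.** Cohorts of about 10 to 30 randomised 1:1 give about 5 to 15 women per arm. The documents give no PCS rate, so 5% to 20% of women meeting a given criterion is an assumption. The chance of at least one such woman in an arm is 1 − (1 − p)^n:

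| n per arm | p = 5% | p = 10% | p = 20% |
|---|---|---|---|
| 5 | 23% | 41% | 67% |
| 10 | 40% | 65% | 89% |
| 15 | 54% | 79% | 96% |

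**6. Effort to count from listings.** In Cohorts 1-5 each woman has 11 + 2 = 13 scheduled post-baseline vital-sign time points (inpatient plus Days 11 and 34) and 4 ECG time points. A 20-woman cohort gives 13 × 20 = 260 vital-sign records and 4 × 20 = 80 ECG records.

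**The case against.** **The AE route already gives counts.** Clinically significant vital-sign and ECG findings must be reported as AEs. TEAEs are tabulated by arm, with separate tables for IP discontinuation and for dose reduction or interruption. Sleepiness levels and C-SSRS answers are also counted. This stands, and it limits the gap to values that meet a criterion but are not reported as AEs.

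**A reader might infer that the SAP contradicts protocol 9.5.7 and should have declared it in 4.1.** The text does not support that. Section 9.5.7 names AE summaries, which the SAP provides. It asks for no table of threshold outliers. The Amendment 7 change table shows that the AE wording came in with that amendment, so the route looks deliberate. What remains is that the SAP does not say how its PCS criteria relate to the protocol's term.

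**A reader might argue that arm means hide a single large excursion.** The SAP does not report means alone. If a large change is the analysed value at a time point, it appears as that arm's minimum or maximum. The point therefore rests on steps 2 to 4 above, which minimum and maximum do not answer.

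**Counts this small are imprecise.** A result of 1/10 versus 0/10 gives a Fisher p-value of 1.0 and exact 95% intervals of roughly 0-45% and 0-31%. This stands as a caution against testing. It is no reason to omit a description from a descriptive trial.

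**Dose decisions use other tables.** The DRC works from its own outputs, specified in a separate document that is not available here and may include outlier counts. Nothing can be concluded about what the DRC sees.

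**Conclusion.** The point holds for the outputs that the SAP itself plans. PCS criteria are fixed in advance and used only as listing flags. A woman who meets one without an AE report is counted nowhere by arm, and the by-time-point statistics cannot recover the count. At the planned arm sizes and the assumed 5% to 20% rates, an arm will often contain at least one such woman, so an empty table is not the likely outcome.

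Two further readings go beyond the documents. A reader might call safety the primary objective; it is listed first, but neither document labels it primary. A reader might also want all ganaxolone pooled against all placebo. That would mix 60-hour infusions with a 6-hour infusion followed by 28 days of capsules and a taper, on different assessment schedules.

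The conclusion assumes that the Appendix 3 output list is complete for vital signs and ECG. It is a cheap improvement to reporting and does not show an error in the safety data to be collected.

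**What to change.** - Add two Safety Set tables, one for vital signs (SAP Table 3) and one for ECG (SAP Table 4): n (%) of women with at least one post-baseline value meeting each criterion, by arm within cohort. Percentages can use the number exposed, as SAP 12.0 already sets.
- Derive these counts from all post-baseline records, including unscheduled and repeat ones, and not from the latest value in each window.
- In the ECG table, also count women meeting the QTcF conditions as written in protocol 4.4.1: above 530 msec, or a rise above 60 msec to a value above 480 msec, with the confirmation on repeat ECG described there. The only QTcF criterion in SAP Table 4 is a prolongation above 30 msec, so the existing flags do not isolate these women.
- State in SAP 12.6 how PCS flags relate to the potentially clinically important findings of protocol 9.5.7, and add both tables to Appendix 3.

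The Table 3 and Table 4 flags are already to be derived for the listings, so the cost is two tables, one extra QTcF derivation and a short text change. The only downside is a little more programming.
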